**Management portals:**

- *Administrator portal:* Study staff will manage participant interactions through a web-based interface that exchanges data directly with the eP app. Study staff will use the participant management system to securely exchange messages with participants using the eP app. The participant management system will have a dashboard to manage and track participant completion of study-related activities, such as survey completion or scheduling of telemedicine consultations.
- *Clinician portal:* Clinicians will view clinically-relevant participant information in a web-based interface that exchanges data with the administrator interface and the eP app. Participant information viewable to clinicians will include lab results and participant self-reports of sexual behavior, PrEP adherence, and PrEP side effects. A calendaring function will be used by clinicians to make time slots available for telemedicine consultations so that participants can schedule through the eP app. Telemedicine consultation data, including clinician notes, will be collected in the clinician interface for each telemedicine consultation.

**Home Test Kit:**

ePrEP will use a mail-based specimen self-collection system that has previously been pilot-tested.[16] Participants will receive a plain box via standard mail that includes instructions and materials for each specimen to be collected. Participants will be provided with video and written instructions as well as a call-in help line for the home collection system (during business hours). After specimen collection, participants will enclose them in a prepaid mailer to be sent directly to the lab. Testing of all specimens will be performed at CLIA-certified laboratories using FDA-approved tests. (Section 5.5)

**Telemedicine:**

The eP app includes a secure video component that will allow for study telemedicine consultations between study clinicians and participants. This will allow study clinicians to evaluate participants at standard, quarterly prescribing intervals for PrEP. Participants may also ask questions of their study clinician using the eP secure messaging system.

#### 5.4.2 PrEP Initiation/Continuation

If laboratory, clinical and behavioral survey results do not show contraindications to PrEP initiation/continuation, the study clinician will initiate or renew the PrEP prescription. Eligible participants will be initiated with a 3-month prescription for FTC/TDF or FTC/TAF by the site study clinician. Standard PrEP financial navigation services will be delivered by study staff trained in order to ensure uniformity of intervention provision. The navigation will use Gilead medication assistance and co-pay access programs, in addition to state-specific programs, to facilitate access to PrEP at low or no cost to participants. We will seek to make home delivery of PrEP prescriptions from pharmacies available. If a participant's insurance does not allow for the home delivery, participants will pick up PrEP from their preferred local pharmacy. Enrolled participants not on PrEP, due to discontinuation or never having initiated, will continue participation in the scheduled research assessments. With clinician guidance, such participants can choose to uptake PrEP at any point during the study.

#### 5.4.3 PrEP Discontinuation / Restart

Regular study interactions include telemedicine consultation, surveys, and messaging with staff. If through any of these interactions a participant reports a gap of not taking PrEP for  $\geq 10$  days, this will be defined as a PrEP discontinuation. Participants who have discontinued PrEP will be

allowed to re-initiate during the study with clinical re-evaluation and repeat HIV testing. An additional creatinine test will not be needed as long as previous results were within acceptable range in the past 6 months. Reasons for discontinuing or restarting will be captured.

#### 5.4.4 Research Staff Training

Study staff and clinicians will complete HSP and GCP training. Staff will be trained on using the ePrEP web-based portal for participant management, and on eP app functionality. Study clinicians will discuss case scenarios for PrEP patients for more standardized approaches to specific scenarios seen by PrEP clinicians.

#### 5.4.5 Intervention Monitoring/Quality Control

The principal investigator will monitor data collection throughout the study, will ensure that protocols and procedures are followed, all adverse event reports are reviewed (if any), confidentiality procedures are implemented, and the UNC IRB is alerted if unexpected concerns arise. The study may also be subject to a quality assurance audit by the sponsor or its designees, as well as inspection by appropriate regulatory authorities.

### 5.5 Laboratory Procedures

All study lab tests will be conducted at CLIA-certified laboratories using FDA-approved tests. Participants will self-collect whole blood in microtubes from finger prick for creatinine and syphilis (using antibody test with reflexive RPR) tests. Whole blood collected on dried blood spot (DBS) cards will be used for HIV testing. Pharyngeal swabs, rectal swabs and a urine sample will be collected for gonorrhea and chlamydia testing. Hepatitis B surface antigen will be tested either through Quest/LabCorp, local health department, or self-collect. Participants may be referred to local testing services, if needed. The Alabama Department of Public Health, Georgia Department of Public Health, Mississippi State Department of Health, and the North Carolina Department of Health and Human Services will be notified of confirmed positive results in accordance with state public health reporting laws, a procedure that will be explained to participants at consent.

*Baseline testing:* All participants will be tested for HIV, syphilis, creatinine, gonorrhea, chlamydia, and Hepatitis B.

*Follow-up testing:* Intervention participants will be tested for HIV, syphilis, gonorrhea, and chlamydia quarterly. Creatinine will be tested at months 3 and 9. All participants are scheduled to return DBS cards for TFV-DP testing at months 6 and 12.

#### 5.5.1 HIV Testing

HIV testing may be conducted on either whole blood or DBS. 4th generation HIV tests will be conducted using DBS cards that participants self-collect through finger prick. Standard of care 3rd generation tests may be run if unable to conduct 4th gen test on DBS sample. Specimens with a reactive result on the antibody-based test will undergo confirmatory testing per established protocols on DBS specimens. If confirmed, results will be returned to participants by study staff experienced in HIV care linkage.

#### 5.5.2 STI Testing

All participants will be tested for syphilis and pharyngeal, urethral, and rectal gonorrhea and chlamydia at Baseline. Intervention participants will be tested for syphilis gonorrhea, and chlamydia (pharyngeal, urethral and rectal) at quarterly follow-up virtual visits. Reflexive RPR titer will be conducted if the syphilis antibody test is reactive. Hepatitis B surface antigen will be tested to determine chronic hepatitis B status at Baseline.

#### 5.5.3 Safety Labs

Creatinine will be checked at Baseline, in order to calculate creatinine clearance for eligibility determination. Creatinine testing will be repeated at months 3 and 9 in accordance with CDC guidance. Creatinine will be tested from participant self-collected whole blood specimens using a point-of-care machine. Creatinine clearance will be calculated using the Cockcroft-Gault equation, with participant's self-reported weight at baseline. If creatinine clearance <60 ml/min on follow-up testing, the prescribing physician will make an assessment and recommendation regarding whether the participant will need repeat testing and/or temporary or permanent discontinuation of PrEP.

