#### 5.5.5 Referrals

In the case of an initial (4th gen) positive HIV test done through the study, participants will be instructed to discontinue PrEP dosing. Participants testing positive will be referred for study-provided HIV confirmatory testing. Upon receipt of positive HIV confirmatory test results, the linkage to care process will be initiated within two business days. For changes in creatinine clearance, study clinicians will consider discontinuing PrEP for any participants with calculated creatinine clearance below 60 ml/min. As needed, the linkage to care process for low creatinine results will be initiated within two business days. For positive STI tests, participants will have PrEP prescriptions initiated or renewed, and be referred to STI treatment at a local agency. Site study staff will follow-up with participants testing positive for STI to encourage participants to seek appropriate care. Laboratory test results will be provided to participant providers if requested and authorized to release.

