#### 6.1.3 On-Study measures

- 1-Month CRF: Intervention participants will have a telemedicine consultation with study staff or clinician to assess experiences one month after initiating PrEP. CRF will record adherence and side effects.
- Surveys for participants in both arms at months 3, 6, 9 and 12: categories include sexual behavior, PrEP cascade, and the validated system usability scale (SUS).

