## 9.0 MONITORING UNTOWARD EFFECTS ASSOCIATED WITH OR RESULTING FROM STUDY

The study will have study clinicians prescribing FDA-approved oral PrEP, in accordance with Gilead's label indications for tenofovir disoproxil fumarate/ emtricitabine (Truvada) or emtricitabine/ tenofovir alafenamide (Descovy). The prescription of PrEP in the study will also follow guidance from the US Public Health Service and US Centers for Disease Control and Prevention. The study will not be providing study drug. Individuals will be getting prescribed medications from a local pharmacy. Side effects due to the medication will be monitored but not considered study-related adverse events.

The frequency and severity of side effects from Truvada and Descovy are listed as follows (items in bold are from the package insert):

- *Very Common (approximate incidence > 50%):* none
- *Common (approximate incidence > 25 - 50%):* none
- *Likely (approximate incidence of > 10 - 25%) and Mild to Moderate (no disruption to temporary interference with daily activities; may include prescription intervention):* **nausea, fatigue, headache, dizziness, depression, insomnia, abnormal dreams, and rash.**
- *Infrequent (approximate incidence of > 1 - 10%) and Mild to Moderate (temporary interference with daily activities; may include prescription intervention) :* **diarrhea, abdominal pain, decrease in weight**, generalized weakness, shortness of breath, increased cough, runny nose, allergic reaction, skin darkening of the palms of hands and/or soles of feet, muscle pain and weakness.
- *Rare (approximate incidence < 1%) and Severe to Life threatening: bone pain and bone changes,* worsening or new kidney damage or failure, liver problems, increases in pancreatic enzyme, increased triglycerides, increased creatine phosphokinase (CPK) which could mean muscle damage, lactic acidosis and severe hepatomegaly with steatosis that may result in liver failure

Site staff must first follow their own IRB's procedure for reporting and managing untoward effects.

There are two types of untoward effects to be identified: (1) those related to the participant and (2) those related to the study staff.

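### Section 5.5.3 names only baseline weight for creatinine clearance, so the month 3 and 9 checks against 60 ml/min would most naturally use an outdated weight

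*Combined protocol and SAP*

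**What the plan says.** Section 5.5.3 first has creatinine checked at baseline for eligibility, then repeated at months 3 and 9. It next gives its only calculation rule: Cockcroft-Gault "with participant's self-reported weight at baseline". The sentence after that sets the follow-up rule. If clearance is below 60 ml/min "on follow-up testing, the prescribing physician will make an assessment and recommendation" on repeat testing or on stopping PrEP for a time or for good. Section 5.5.5 repeats the threshold: "study clinicians will consider discontinuing PrEP for any participants with calculated creatinine clearance below 60 ml/min".

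Section 5.5 gives the same schedule, "Creatinine will be tested at months 3 and 9", in its follow-up paragraph, directly after the sentence on quarterly testing of intervention participants. Section 8.1 gives control participants only surveys and dried blood spot cards after baseline.

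Section 5.4.3 waives a new creatinine test when PrEP is restarted, "as long as previous results were within acceptable range in the past 6 months". Section 9.0 has the Safety Monitoring Committee (SMC) follow changes in kidney function, and section 10.3.1 lists renal function among the safety measures.

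**The concern.** A baseline weight is right for the eligibility calculation. At month 3 or 9 it is out of date, and the result is then compared with a fixed number that triggers clinical action. The two directions of error are not equally serious. Weight gain makes the calculated clearance too low and causes an unneeded review. Weight loss makes it too high and can hide a value below 60. Loss is also a plausible event here, because section 9.0 lists "diarrhea, abdominal pain, decrease in weight" among the infrequent side effects (above 1% to 10%) of the prescribed drugs.

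At stake is the prompt for clinician review and for considering whether to stop PrEP. If the restart waiver or the renal summaries rest on clearance, the same error reaches them too. Care in this arm is remote, so no study visit yields a measured weight by default. The protocol has to ask for one.

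**Working it through.** **Which weight applies.** The order of statements in section 5.5.3 is: baseline test, repeat tests at months 3 and 9, specimen and device, calculation rule with baseline weight, follow-up threshold. The rule comes after the repeat tests are introduced and directly before the threshold that uses its result. Nothing limits it to eligibility.

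No other section supplies a later weight. The follow-up testing paragraph (5.5), the on-study measures (6.1.3 and 6.2.2) and the tracking section (8.1) name none. The clinician portal description does not either: "Participant information viewable to clinicians will include lab results and participant self-reports of sexual behavior, PrEP adherence, and PrEP side effects". The lists in 6.1.3 and in the portal description are not worded as complete, so this shows that no follow-up weight is stated, not that none is collected.

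**Formula.** The protocol names Cockcroft-Gault without printing it. For men, with creatinine in mg/dL:

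clearance = (140 − age) × weight / (72 × creatinine)

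If weight has changed by a fraction d since baseline, then

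- baseline-weight value / current-weight value = 1/(1 + d)
- current-weight value when the baseline-weight value is exactly 60 = 60 × (1 + d)

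**Inputs.** The threshold of 60 ml/min (5.5.3, 5.5.5) and the age range 18-29 (4.1) come from the protocol. The weight changes are assumptions, since the documents give none.

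| Assumed change d | Error in calculated clearance | 60 × (1 + d) | Consequence |
|---|---|---|---|
| −5% | 1/0.95 = +5.3% | 57 | current-weight values of 57 to 60 not flagged |
| −10% | 1/0.90 = +11.1% | 54 | 54 to 60 not flagged |
| −15% | 1/0.85 = +17.6% | 51 | 51 to 60 not flagged |
| +5% | 1/1.05 = −4.8% | 63 | 60 to 63 flagged needlessly |
| +10% | 1/1.10 = −9.1% | 66 | 60 to 66 flagged needlessly |

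**In creatinine terms.** Take an assumed man of 25 who weighed 70 kg at baseline. Clearance equals 60 when creatinine = (140 − 25) × weight / (72 × 60) = 115 × weight / 4320.

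- Baseline weight, 70 kg: 115 × 70 / 4320 = 1.86 mg/dL
- After a 5% loss, 66.5 kg: 1.77 mg/dL
- After a 10% loss, 63.0 kg: 1.68 mg/dL
- After a 15% loss, 59.5 kg: 1.58 mg/dL

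Creatinine between the current-weight figure and 1.86 would go unflagged.

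**How rare this is.** At a creatinine of 1.0 mg/dL the same man has a clearance of 115 × 70 / 72 = 112 ml/min. Measured from that value, creatinine would have to rise by 58% to 86% to lie between 1.58 and 1.86, and the weight loss would have to occur as well.

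**The case against.** The strongest reply is that the fault is inferred. Section 5.5.3 opens by tying the baseline creatinine to eligibility, so the weight phrase may have been meant for that calculation alone. That reading is possible, but it leaves the follow-up weight unspecified while a numeric safety rule depends on it. The sentence would need clarifying either way. The survey instruments and case report forms are not in these documents, so a follow-up weight may already be collected. That stands, and it would shorten the fix.

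The safeguards also stand. Section 5.4.2 renews PrEP only when laboratory, clinical and survey results together show no contraindication. Clinicians see laboratory results and reported side effects, and section 8.1 gives consultations at months 1, 3, 6, 9 and 12. Falling below 60 prompts an assessment, and nothing prevents review of a higher value.

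Two limits on the evidence stand as well. The side-effect rate in section 9.0 says how often weight falls, not by how much, so it does not support the 5% to 15% range used above. And the restart waiver, the SMC monitoring and section 10.3.1 do not define their renal measure as calculated clearance, so an effect on them is conditional.

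Finally, a fixed weight has one merit: serial clearance then tracks creatinine alone. That argues for showing creatinine separately. It does not make an old weight right for judging clearance on the day.

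**Conclusion.** The concern holds, at low importance. As written, the plan's only weight rule carries the baseline value into a follow-up safety threshold. For assumed losses of 5% to 15%, calculated clearance is overstated by 5.3% to 17.6%, and current-weight values as low as 57 to 51 ml/min escape the trigger. For assumed gains of 5% to 10%, it is understated by 4.8% to 9.1%, which causes only extra reviews. The net direction in this trial is unknown, because the documents give no weight-change data, and few men aged 18-29 will be near the threshold.

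Follow-up creatinine is in effect intervention-arm monitoring. The primary outcome, alpha, power and between-arm comparison are unaffected.

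**What to change.** Add a self-reported current-weight question at months 3 and 9 for participants having creatinine tests. State in section 5.5.3 that each clearance calculation uses the weight reported at that visit, and that baseline weight serves the eligibility calculation only. Changes in clearance will then reflect weight as well as creatinine, so report serum creatinine beside clearance in the SMC and final renal summaries. Leave the 60 ml/min threshold and the clinical response as they are.

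The cost is one survey item at two visits, one protocol sentence and one added column in a safety table. If follow-up weight is already collected on a form outside these documents, no new item is needed and the protocol change is that one sentence in 5.5.3.

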#### 5.5.4 Dried Blood Spots

Participants will be informed of expectations regarding specimen collection at baseline. DBS cards will be sent to both intervention and control participants for primary outcome assessment at 6 months and 12 months. Spots will be collected on a filter paper card and dried for  $\geq 4$  hours prior to mailing. Once returned to the lab, the primary outcome assessment DBS specimens will be stored in a laboratory freezer at  $-20^{\circ}\text{C}$  until they are batch tested for TFV-DP levels at the UNC [name] Lab. The [name] Laboratory will also measure emtricitabine-triphosphate (FTC-TP) from the DBS cards for secondary analyses.

#### 5.5.5 Referrals

In the case of an initial (4th gen) positive HIV test done through the study, participants will be instructed to discontinue PrEP dosing. Participants testing positive will be referred for study-provided HIV confirmatory testing. Upon receipt of positive HIV confirmatory test results, the linkage to care process will be initiated within two business days. For changes in creatinine clearance, study clinicians will consider discontinuing PrEP for any participants with calculated creatinine clearance below 60 ml/min. As needed, the linkage to care process for low creatinine results will be initiated within two business days. For positive STI tests, participants will have PrEP prescriptions initiated or renewed, and be referred to STI treatment at a local agency. Site study staff will follow-up with participants testing positive for STI to encourage participants to seek appropriate care. Laboratory test results will be provided to participant providers if requested and authorized to release.

## 6.0 MEASURES

### 6.1 Behavioral Measures

#### 6.1.1 Pre-entry or screening measures

- Screener for Behavioral Eligibility: The screener asks basic demographic questions and behavioral eligibility questions.

#### 6.1.2 Pre-intervention (baseline) measures

- Baseline Survey: The baseline survey will include questions in the domains of demographics, sexual history, potential correlates of initiating and maintaining in PrEP care, mental health, and stigma. To continue to be eligible for randomization, all survey modules must be completed within a week of starting the first module. After completing the baseline survey (and if clinically eligible) participant will be randomized into control or intervention arm.

#### 6.1.3 On-Study measures

- 1-Month CRF: Intervention participants will have a telemedicine consultation with study staff or clinician to assess experiences one month after initiating PrEP. CRF will record adherence and side effects.
- Surveys for participants in both arms at months 3, 6, 9 and 12: categories include sexual behavior, PrEP cascade, and the validated system usability scale (SUS).

#### 6.1.4 Premature Discontinuation/Off-Study measures

Participants will be asked to answer several brief questions, to be recorded on a CRF, documenting reasons for study withdrawal.

### 6.2 Clinical and Laboratory Evaluations

#### 6.2.1 Baseline measures

- Home Test Kit: HIV, and Creatinine tests will determine clinical eligibility for the study.

#### 6.2.2 On-Study measures

- *HIV*: 4th generation HIV tests will be conducted using whole blood specimen. HIV testing will be conducted quarterly.
- *DBS*: TFV-DP levels will be assessed at months 6 and 12 to gain an understanding of participant adherence to their PrEP regime. These research outcome results will not be returned to the participants or clinicians.

## 7.0 DATA COLLECTION AND SITE MONITORING

### 7.1 Development of Protocol and Case Report Forms

The Protocol Team, in collaboration with the Management Core (MC) and Analytic Core (AC), is responsible for the development of this protocol and the Case Report Forms (CRFs) needed to collect the information required to implement this protocol.

### 7.2 Data Records

Participant-related study information will be identified through a study ID number (SID) and participant code (participant first initial and two-digit day of birth) on all participant CRFs and survey data. SID will be used wherever possible in place of personally-identifying information.

Source documents, such as laboratory results, the clinician dashboard, and CRFs, will be accessible only to the study staff and study clinicians on a role-based standard.

SIDs will not be entered into the mobile app and instead a unique app ID will be assigned to each participant and used when logging into the app. These unique App IDs will be provided by the developer. Participant locator/contact information will be stored securely in the web-based interface (Section 7.3.4).

